11.4 Recording of Data

A CRF is required and must be completed for each subject by qualified and authorized personnel. All data on the CRF must reflect the corresponding source document, except when a section of the CRF itself is used as the source document. Any correction to entries made on the CRF must be documented in a valid audit trail where the correction is dated, the individual making the correction is identified, the reason for the change is stated, and the original data are not obscured. Only data required by the protocol for the purposes of the study should be collected.

The investigator must sign each CRF. The investigator will report the CRFs to the sponsor and retain a copy of the CRFs.

11.5 Identification of Source Data

All data to be recorded on the CRF must reflect the corresponding source documents. For the following item(s), the data recorded directly on the CRF are to be considered source data:

- Study drug compliance (eg, the reason for dose reduction).
- Discontinuation information.
- Comments and other information on AEs (eg, severity, relationship to study drug, outcome).

11.6 Retention of Records

The circumstances of completion or termination of the study notwithstanding, the investigator (or if regionally required, the head of the medical institution or the designated representative) is responsible for retaining all study documents, including but not limited to the protocol, copies of CRFs, the Investigator's Brochure, and regulatory agency registration documents (eg, Form FDA 1572 ICFs, and IRB/IEC correspondence). The site should plan to retain study documents, as directed by the sponsor, for at least 2 years after the last approval of a marketing application in an ICH region and until there are no pending or contemplated marketing applications in an ICH region or at least 3 years have elapsed since the formal discontinuation of clinical development of the investigational product.

It is requested that at the completion of the required retention period, or should the investigator retire or relocate, the investigator contact the sponsor, allowing the sponsor the option of permanently retaining the study records.

11.7 Auditing Procedures and Inspection

In addition to routine monitoring procedures, the sponsor's Clinical Quality Assurance department conducts audits of clinical research activities in accordance with the sponsor's SOPs to evaluate compliance with the principles of ICH GCP and all applicable local regulations. If a government regulatory authority requests an inspection during the study or after its completion, the investigator must inform the sponsor immediately.

11.8 Handling of Study Drug

All study drug(s) will be supplied to the principal investigator (or a designated pharmacist) by the sponsor, or when there is agreement between the PI and sponsor, the site can source study drug if it is commercially available in the country and be reimbursed by the sponsor. Drug supplies must be kept in an appropriate secure area (eg, locked cabinet) and stored according to the conditions specified on the drug labels. The investigator (or a designated pharmacist) must maintain an accurate record of the shipment and dispensing of the study drug in a drug accountability ledger, a copy of which must be given to the sponsor at the end of the study. An accurate record of the date and amount of study drug dispensed to each subject must be available for inspection at any time. The CRA will visit the site and review these documents along with all other study conduct documents at appropriate intervals once study drug has been received by the site.

All drug supplies are to be used only for this study and not for any other purpose. The investigator (or site personnel) must not destroy any drug labels or any partly used or unused drug supply before approval to do so by the sponsor. At the conclusion of the study and as appropriate during the study, the investigator (or a designated pharmacist) will return all used and unused drug containers, drug labels, and a copy of the completed drug disposition form to the sponsor's CRA or, when approval is given by the sponsor, will destroy supplies and containers at the site.

11.9 Publication of Results

All manuscripts, abstracts, or other modes of presentation arising from the results of the study must be reviewed and approved in writing by the sponsor in advance of submission pursuant to the terms and conditions set forth in the executed Clinical Trial Agreement between the sponsor/CRO and the institution/investigator. The review is aimed at protecting the sponsor's proprietary information existing either at the date of the commencement of the study or generated during the study.

The detailed obligations regarding the publication of any data, material results, or other information generated or created in relation to the study shall be set out in the agreement between each investigator and the sponsor or CRO, as appropriate.

11.10 Disclosure and Confidentiality

The contents of this protocol and any amendments and results obtained during the study should be kept confidential by the investigator, the investigator's staff, and the IRB/IEC and will not be disclosed in whole or in part to others, or used for any purpose other than reviewing or performing the study, without the written consent of the sponsor. No data collected as part of this study will be used in any written work, including publications, without the written consent of the sponsor. These obligations of confidentiality and non-use shall in no way diminish such obligations as set forth in either the Confidentiality Agreement or Clinical Trial Agreement executed between the sponsor/CRO and the institution/investigator.

All persons assisting in the performance of this study must be bound by the obligations of confidentiality and non-use set forth in either the Confidentiality Agreement or Clinical Trial Agreement executed between the institution/investigator and the sponsor/CRO.

11.11 Discontinuation of Study

The sponsor reserves the right to discontinue the study for medical reasons or any other reason at any time. If a study is prematurely terminated or suspended, the sponsor will promptly inform the investigators/institutions and regulatory authorities of the termination or suspension and the reason(s) for the termination or suspension. The IRB/IEC will also be informed promptly and provided the reason(s) for the termination or suspension by the sponsor or by the investigator/institution, as specified by the applicable regulatory requirement(s).

The investigator reserves the right to discontinue the study should his/her judgment so dictate. If the investigator terminates or suspends a study without prior agreement of the sponsor, the investigator should inform the institution where applicable, and the investigator/institution should promptly inform the sponsor and the IRB/IEC and provide the sponsor and the IRB/IEC with a detailed written explanation of the termination or suspension. Study records must be retained as noted above.

11.12 Subject Insurance and Indemnity

The sponsor will provide insurance for any subjects participating in the study in accordance with all applicable laws and regulations.

Appendix 1 Clinical Studies Evaluating Drug-Drug Interactions with Lenvatinib

Nonclinical studies identify CYP3A4 as a potentially important Cytochrome P450 isozyme responsible for metabolism of lenvatinib. Clinical studies were conducted to test these findings. Simultaneous CYP3A4/P-glycoprotein (P-gp) inhibition by ketoconazole slightly (15% to19%) increases systemic exposure to lenvatinib (Shumaker, et al., 2015). Since no change was observed in half-life, tmax, or lag time (tlag), the slight increase in systemic exposure is probably related to a decrease in first pass metabolism. However, since the magnitude of change is small, co-administration of lenvatinib with CYP3A4/P-gp inhibitors is not of clinical concern. The influence of P-gp inhibition on lenvatinib PK has been investigated. P-gp inhibition was accomplished by co-administering a single dose of rifampin with a single dose of lenvatinib. Preliminary results suggest P-gp inhibition increases systemic exposure to lenvatinib 26% to 32%. Thus, co-administration of lenvatinib with P-gp inhibitors only causes a small increase in lenvatinib exposure.

The influence of simultaneous P-gp and CYP3A4 induction on lenvatinib PK has been investigated. Examination of simultaneous P-gp and CYP3A4 induction on lenvatinib PK was accomplished by administering rifampin QD for 21 days (Shumaker, et al., 2014). A single dose of lenvatinib was co-administered with the 15th dose of rifampin. Based on preliminary data, simultaneous P-gp and CYP3A4 induction minimally altered lenvatinib exposure as mean C_{max} increased about 8% while AUC decreased about 7%.

Coadministration of lenvatinib with CYP3A4/P-gp inducers is not of clinical concern. The main metabolic pathways for lenvatinib in humans were identified as enzymatic (CYP3A and aldehyde oxidase) and non-enzymatic processes (Lenvima® Package Insert).

Appendix 2 Common Terminology Criteria for Adverse Events (CTCAE) Version 4.03

Common Terminology Criteria for Adverse Events (CTCAE v4.03, published 14 Jun 2010) provides descriptive terminology to be used for adverse event reporting in clinical studies. A brief definition is provided to clarify the meaning of each AE term. To increase the accuracy of AE reporting, all adverse event terms in CTCAE v4.03 have been correlated with single-concept Medical Dictionary for Regulatory Activities (MedDRA) terms.

Common Terminology Criteria for Adverse Events v4.03 grading refers to the severity of the AE. The Common Terminology Criteria for Adverse Events grades 1 through 5, with unique clinical descriptions of severity for each AE, are based on this general guideline:

Grade	CTCAE Status
1	Mild: asymptomatic or mild symptoms; clinical or diagnostic observations only; intervention not indicated
2	Moderate: minimal, local, or noninvasive intervention indicated; limiting age- appropriate instrumental activities of daily living (ADL) ^a
3	Severe or medically significant but not immediately life-threatening: hospitalization or prolongation of hospitalization indicated; disabling, limiting self-care ADL ^b
4	Life-threatening consequences: urgent intervention indicated
5	Death related to adverse event

ADL = activities of daily living, CTCAE = Common Terminology Criteria for Adverse Events.

- a: Instrumental ADL refers to preparing meals, shopping for groceries or clothes, using the telephone, managing money, etc.
- b: Self-care ADL refers to bathing, dressing and undressing, feeding self, using the toilet, taking medications, and not bedridden.

Adapted from the NCI, Cancer Therapy Evaluation Program. CTCAE v4.03

For further details regarding MedDRA, refer to the MedDRA website at: http://www.meddra.org

Appendix 3 Sponsor's Grading for Laboratory Values Common Terminology Criteria for Adverse Events (CTCAE) Version 4.03

	Grade 1	Grade 2	Grade 3	Grade 4
BLOOD/BONE MARROW				
Hemoglobin	<lln 10.0="" dl
<lln 100="" g="" l
<lln 6.2="" l<="" mmol="" td="" –=""><10.0 - 8.0 g/dL <100 - 80 g/L <6.2 - 4.9 mmol/L	<8.0 g/dL <80 g/L <4.9 mmol/L; transfusion indicated	life-threatening consequences; urgent intervention indicated	</lln></lln></lln>	<10.0 - 8.0 g/dL <100 - 80 g/L <6.2 - 4.9 mmol/L	<8.0 g/dL <80 g/L <4.9 mmol/L; transfusion indicated	life-threatening consequences; urgent intervention indicated
Leukocytes (total WBC)	<lln -="" 3.0×109/L <lln -="" 3000="" mm3</lln></lln>	<3.0 - 2.0×10 ⁹ /L <3000 - 2000/mm ³	$ \begin{array}{l} <2.0-1.0{\times}10^9/L \\ <2000-1000/mm^3 \end{array} $	<1.0×10 ⁹ /L <1000/mm ³
Lymphocytes	<lln -="" 800="" mm3 <lln -="" 0.8×109/L</lln></lln>	$ \begin{array}{l} < \!\!800 - 500 / mm^3 \\ < \!\!0.8 - 0.5 \!\times\! 10^9 / L \end{array} $		<200/mm ³ <0.2×10 ⁹ /L
Neutrophils	<lln -="" 1.5×109/L <lln -="" 1500="" mm3</lln></lln>	<1.5 - 1.0×10 ⁹ /L <1500 - 1000/mm ³	<1.0 - 0.5×10 ⁹ /L <1000 - 500/mm ³	<0.5×10 ⁹ /L <500/mm ³
Platelets	<lln -="" 75.0×109/L <lln -="" 75,000="" mm3</lln></lln>	<75.0 - 50.0×10 ⁹ /L <75,000 - 50,000/mm ³	$ \begin{array}{l} < 50.0 - 25.0 \times 10^9 / L \\ < 50,000 - 25,000 / mm^3 \end{array} $	<25.0×10 ⁹ /L <25,000/mm ³
METABOLIC/LABORATORY				
Albumin, serum- low (hypoalbuminemia)	<lln 3="" dl
<lln 30="" g="" l<="" td="" –=""><3 - 2 g/dL <30 - 20 g/L	<2 g/dL <20 g/L	life-threatening consequences; urgent intervention indicated	</lln></lln>	<3 - 2 g/dL <30 - 20 g/L	<2 g/dL <20 g/L	life-threatening consequences; urgent intervention indicated
Alkaline phosphatase	>ULN-2.5×ULN	>2.5-5.0×ULN	>5.0-20.0×ULN	>20.0×ULN
ALT	>ULN-3.0×ULN	>3.0-5.0×ULN	>5.0-20.0×ULN	>20.0×ULN
AST	>ULN-3.0×ULN	>3.0-5.0×ULN	>5.0-20.0×ULN	>20.0×ULN
Bilirubin (hyperbilirubinemia)	>ULN-1.5×ULN	>1.5-3.0×ULN	>3.0-10.0×ULN	>10.0×ULN
Calcium, serum-low (hypocalcemia)	<lln -="" 8.0="" dl
<lln -="" 2.0="" l<="" mmol="" td=""><8.0 - 7.0 mg/dL <2.0 - 1.75 mmol/L	<7.0 - 6.0 mg/dL <1.75 - 1.5 mmol/L	<6.0 mg/dL <1.5 mmol/L	</lln></lln>	<8.0 - 7.0 mg/dL <2.0 - 1.75 mmol/L	<7.0 - 6.0 mg/dL <1.75 - 1.5 mmol/L	<6.0 mg/dL <1.5 mmol/L
Calcium, serum-high (hypercalcemia)	>ULN – 11.5 mg/dL >ULN – 2.9 mmol/L	>11.5 - 12.5 mg/dL >2.9 - 3.1 mmol/L	>12.5 - 13.5 mg/dL >3.1 - 3.4 mmol/L	>13.5 mg/dL >3.4 mmol/L
Cholesterol, serum-high (hypercholesterolemia)	>ULN - 300 mg/dL >ULN - 7.75 mmol/L	>300 - 400 mg/dL >7.75 - 10.34 mmol/L	>400 - 500 mg/dL >10.34 - 12.92 mmol/L	>500 mg/dL >12.92 mmol/L
Creatinine	>ULN-1.5×ULN	>1.5-3.0×ULN	>3.0-6.0×ULN	>6.0×ULN
GGT (γ-glutamyl transpeptidase)	>ULN-2.5×ULN	>2.5-5.0×ULN	>5.0-20.0×ULN	>20.0×ULN
Glucose, serum-high (hyperglycemia)	Fasting glucose value: >ULN – 160 mg/dL >ULN – 8.9 mmol/L	Fasting glucose value: >160 – 250 mg/dL >8.9 – 13.9 mmol/L	>250 – 500 mg/dL; >13.9 – 27.8 mmol/L; hospitalization indicated	>500 mg/dL; >27.8 mmol/L; life-threatening consequences
Glucose, serum-low (hypoglycemia)	<lln -="" 55="" dl
<lln -="" 3.0="" l<="" mmol="" td=""><55 – 40 mg/dL <3.0 – 2.2 mmol/L	<40 – 30 mg/dL <2.2 – 1.7 mmol/L	<30 mg/dL <1.7 mmol/L	</lln></lln>	<55 – 40 mg/dL <3.0 – 2.2 mmol/L	<40 – 30 mg/dL <2.2 – 1.7 mmol/L	<30 mg/dL <1.7 mmol/L

Sponsor's Grading for Laboratory Values

	Grade 1	Grade 2	Grade 3	Grade 4
				life-threatening consequences; seizures
Phosphate, serum-low (hypophosphatemia)	<lln 2.5="" dl
<lln 0.8="" l<="" mmol="" td="" –=""><2.5 – 2.0 mg/dL <0.8 – 0.6 mmol/L	<2.0 – 1.0 mg/dL <0.6 – 0.3 mmol/L	<1.0 mg/dL <0.3 mmol/L life-threatening consequences	</lln></lln>	<2.5 – 2.0 mg/dL <0.8 – 0.6 mmol/L	<2.0 – 1.0 mg/dL <0.6 – 0.3 mmol/L	<1.0 mg/dL <0.3 mmol/L life-threatening consequences
Potassium, serum-high (hyperkalemia)	>ULN – 5.5 mmol/L	>5.5 – 6.0 mmol/L	>6.0 – 7.0 mmol/L hospitalization indicated	>7.0 mmol/L life-threatening consequences
Potassium, serum-low (hypokalemia)	<lln 3.0="" l<="" mmol="" td="" –=""><lln 3.0="" l;
symptomatic; intervention indicated</lln>	<3.0 – 2.5 mmol/L hospitalization indicated	<2.5 mmol/L life-threatening consequences	</lln>	<lln 3.0="" l;
symptomatic; intervention indicated</lln>	<3.0 – 2.5 mmol/L hospitalization indicated	<2.5 mmol/L life-threatening consequences
Sodium, serum-high (hypernatremia)	>ULN – 150 mmol/L	>150 – 155 mmol/L	>155 – 160 mmol/L hospitalization indicated	>160 mmol/L life-threatening consequences
Sodium, serum-low (hyponatremia)	<lln 130="" l<="" mmol="" td="" –="">N/A	<130 – 120 mmol/L	<120 mmol/L life-threatening consequences	</lln>	N/A	<130 – 120 mmol/L	<120 mmol/L life-threatening consequences
Triglyceride, serum-high (hypertriglyceridemia)	150 – 300 mg/dL 1.71 – 3.42 mmol/L	>300 - 500 mg/dL >3.42 - 5.7 mmol/L	>500 – 1000 mg/dL >5.7 – 11.4 mmol/L	>1000 mg/dL >11.4 mmol/L life-threatening consequences
Uric acid, serum-high (hyperuricemia)	>ULN – 10 mg/dL ≤0.59 mmol/L without physiologic consequences	N/A	>ULN – 10 mg/dL ≤0.59 mmol/L with physiologic consequences	>10 mg/dL >0.59 mmol/L life-threatening consequences

Sponsor's Grading for Laboratory Values

ALT = alanine aminotransferase (serum glutamic pyruvic transaminase), AST = aspartate aminotransferase (serum glutamic oxaloacetic transaminase), GGT = γ -glutamyl transpeptidase, N/A = not applicable, LLN = lower limit of normal, ULN = upper limit of normal, WBC = white blood cell.

Based on Common Terminology Criteria for Adverse events (CTCAE) Version 4.0. Published: May 28, 2009 (v4.03: June 14, 2010).

2 VERSION HISTORY

Version	Description	Date
1.0	Initial version	05 Jun 2019
2.0	
Revised the scope of the statistical analysis plan to reflect the decision by the team to prepare only 1 clinical study report which would present all analyses by region (China, Rest of World).Clarified that adverse events are considered treatment emergent in this rollover study if they occurred on or after the first dose date of study drug and on or before 28 days after the last dose date of study drug.Reduced the number of TLGs to only present major adverse event categories, eg, TEAEs, treatment-related TEAEs, SAEs, AEs CTCAE Grade ≥ 3, AEs leading to discontinuation.	28 Feb 2024

3 LIST OF ABBREVIATIONS AND DEFINITIONS OF TERMS

Abbreviation	Term
ADaM	Analysis Data Model
AE	adverse event
CTCAE	Common Terminology Criteria for Adverse Events
eCRF	electronic case report form
ICF	informed consent form
MedDRA	Medical Dictionary for Regulatory Activities
PT	preferred term
SAE	serious adverse event
SAP	statistical analysis plan
SD	standard deviation
SOC	system organ class
TEAE	treatment-emergent adverse event
TLG	tables, listings, and graphs
WHO	World Health Organization

4 INTRODUCTION

The purpose of this statistical analysis plan (SAP) is to describe the procedures and the statistical methods that will be used to analyze and report the results for Eisai Protocol E7080-G000-604. This is a long term, open-label extension study to roll over eligible subjects from Eisai-sponsored lenvatinib studies. This study was conducted in China and several other countries including Australia, Belgium, Germany, Italy, Netherlands, Poland, Romania, South Korea, Thailand, and the United States; summaries will be prepared by region (China vs Rest of World) and across all subjects.

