The efficacy and safety of lenvatinib treatment has also been evaluated in the multicenter. randomized, double-blind, placebo-controlled Phase 3 trial E7080-G000-303 (SELECT trial) in patients with RR-DTC with documented disease progression within 13 months. Patients were stratified by age (≤ 65 , > 65 years), region and ≤ 1 prior VEGFR-targeted therapies and randomized 2:1 to lenvatinib or placebo arms (24 mg a day, 28-day cycle). The primary endpoint was PFS assessed by Independent Radiologic Review; the secondary endpoints included ORR (ie, complete response [CR] + partial response [PR]), OS, and safety. A total of 392 patients (63.0 years median age; 51.0% male) were randomized at over 100 sites in Europe, North and South America, and Asia. Patients in the lenvatinib arm had a significantly prolonged PFS (hazard ratio = 0.21, 95% confidence interval [CI] = 0.14-0.31; $P \le 0001$) with a median PFS for the lenvatinib arm of 18.3 months (95% CI = 15.1-not evaluable) vs the placebo arm: 3.6 months (95% CI = 2.2–3.7). The lenvatinib arm PFS benefit was observed in all predefined subgroups: median lenvatinib arm PFS for patients with prior vs no prior VEGF-therapy was 15.1 months (n=66) and 18.7 months (n=195). respectively; rates (n) of CRs for the lenvatinib arm vs placebo arm were 1.5% (4) and 0, respectively; PRs for the lenvatinib arm vs the placebo arm were 63.2% (165) and 1.5% (2), respectively. Median exposure durations for the lenvatinib arm vs the placebo arm were 13.8 months and 3.9 months, respectively; median time to lenvatinib response was 2.0 months. Median OS has not been reached; deaths for the lenvatinib arm were 71 (27.2%) and for the placebo arm were 47 (35.9%). The 5 most common lenvatinib treatment-related adverse events (AEs) (any grade) were hypertension (68%), diarrhea (59%), appetite decreased (50%), weight loss (46%), nausea (41%). The most common Grade \geq 3 lenvatinib treatmentrelated AEs (\geq 5%) were hypertension (42%), proteinuria (10%), weight loss (10%), diarrhea (8%), and appetite decreased (5%). The lenvatinib dose was reduced in 78.5% of patients and lenvatinib was discontinued due to AEs in 14.2% of patients (Schlumberger, et al., 2014). Based on the efficacy and safety information to date, patients with RR-DTC may benefit from lenvatinib treatment.

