9.4 Treatment(s)

9.4.1 Treatment(s) Administered

Subjects enrolled from parent study will enter the roll-over study and will continue the study drug of lenvatinib, or combination regimen, or any other comparator therapy (except placebo) at the same doses upon discontinuation of the parent study. Study drug(s) administered will be recorded in the case report form (CRF).

Subject must not be dispensed more than a 3-months supply of study drug(s) at any particular time during participation in Study E7080-G000-604.

For China Only:

Comparator Drug: Sorafenib

The subject(s) who receive the comparator in the parent study will be enrolled to Cohort C. In the event that comparator clinical supply is limited, the comparator treatment may be obtained commercially from local sources and reimbursed by the sponsor unless this is prohibited by specific country laws. Further instructions on acquisition procedures for commercial supply will be provided by the sponsor.

Criteria for Interruption of Treatment, Dose Reduction and Resumption

Dose reduction and interruptions for subjects who experience toxicity will be made according to the guidelines provided in the parent protocol.

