9.7.1.6 Safety Analyses

All safety analyses will be performed on the Safety Analysis Set. All safety analyses will be summarized separately by treatment group. TEAEs and SAEs will be summarized using descriptive statistics. Time to treatment discontinuation due to a TEAE, number of dose reductions, and time to first dose reduction will be summarized.

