6.3 Data Analysis General Considerations

Descriptive statistics for continuous variables will include the number of subjects, mean, standard deviation (SD), median, Q1, Q3, and range (minimum, maximum). Categorical variables will be summarized by reporting the number and percentage of subjects. In most cases, the denominator for calculating percentages will be the number of subjects in the column header. Whenever a different subset is used to define the denominator, a footnote will be provided to describe the set of subjects to be used as the denominator. The reporting number of decimal places will be provided in the table shells.

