6.5.1 Extent of Exposure

The length of time on treatment (months), and the quantity of study drug administered [dose intensity (mg/day)] will be summarized.

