6.5.2 Adverse Events

The adverse event (AE) verbatim descriptions (investigator terms from the eCRF) will be classified into standardized medical terminology using the Medical Dictionary for Regulatory

Activities (MedDRA). The linked MedDRA preferred term (PT) and primary system organ class (SOC) are also captured in the database.

AEs collected in this study must be treatment-emergent adverse events (TEAE). This is defined as an AE that emerges during treatment in the rollover study, having been absent before the time the subject signs the rollover study ICF or

- Re-emerges during treatment in the rollover study, having been present before signing the ICF but stopped before signing the ICF, or
- Worsens in severity during treatment in the rollover study relative to the pre-ICF state, when the AE is continuous.

Only those AEs that are treatment emergent will be included in summary tables. TEAEs are those occurring on or after the first dose date of study drug and on or before 28 days after the last dose of study drug. All TEAEs will be presented in subject data listings.

An overview table, including the number and percentage of subjects with TEAEs, SAEs, deaths, and those with TEAEs that led to study drug discontinuation, interruption, or dose reduction will be provided. The number (percentage) of subjects with TEAEs will be summarized by SOC and PT, by relationship to study drug (Yes [related] and No [not related]), and by CTCAE toxicity grade as follows:

- Overview of TEAEs
- TEAEs by SOC and PT
- TEAEs by decreasing frequency of PT
- TEAEs with CTCAE Grade ≥ 3 by decreasing incidence of PT
- Treatment-emergent serious AEs by decreasing incidence of PT
- Overview of treatment-related TEAEs
- Treatment-related TEAEs by SOC and PT
- Treatment-related TEAEs by decreasing frequency of PT
- Treatment-related TEAEs with CTCAE Grade ≥ 3 by decreasing incidence of PT
- Treatment-related treatment-emergent serious AEs by decreasing incidence of PT
- Fatal TEAEs by decreasing incidence of PT
- TEAEs leading to treatment discontinuation of lenvatinib

The following listings will be provided for the subjects in the Safety Analysis Set:

- Demographics

- Disposition
- Lenvatinib dosing
- All AEs
- All SAEs
- Adverse events with CTCAE Grade 3 or above
- All AEs leading to study drug discontinuation
- All fatal AEs

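### SAP v2.0 specifies safety summaries by region where the protocol requires them by treatment group, and records no departure, so the specified tables cannot show each regimen's safety

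*SAP*

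**What the plan says.** Protocol 9.7.1.6 sets the grouping rule: "All safety analyses will be summarized separately by treatment group". The protocol's only treatment grouping is the set of treatment cohorts in the Synopsis and in Figure 1 of section 9.1: A (lenvatinib monotherapy), B (lenvatinib combination) and C (active comparator). Protocol 9.5.7.1 counts all three as study drug.

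SAP v2.0, section 4, sets a different rule: "summaries will be prepared by region (China vs Rest of World) and across all subjects". The v2.0 entry in the SAP version history also describes a single study report with every analysis by region. SAP 4.2 lists Cohorts A, B and C, but only as definitions for enrolment. SAP 6.5 names the Safety Analysis Set and does not carry over the treatment-group rule. None of the 12 adverse-event tables listed in SAP 6.5.2 is specified by cohort. SAP 8 states that no changes to the planned analyses are foreseen.

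Three further provisions matter here:

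- Denominators (SAP 6.3): "In most cases, the denominator for calculating percentages will be the number of subjects in the column header". A footnote is required when another subset is used.
- One table in SAP 6.5.2 is specific to a drug: "TEAEs leading to treatment discontinuation of lenvatinib".
- Exposure (SAP 6.5.1): "the quantity of study drug administered [dose intensity (mg/day)] will be summarized", with no statement that this is done per drug.

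**The concern.** The primary objective is descriptive: the long-term safety of the study drug or drugs. When those are different regimens, the useful result is the adverse-event profile of each, and the protocol asked for that. Columns for China, Rest of World and all subjects average over the regimens, so each percentage depends on the cohort mix as well as on the drugs.

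Three consequences follow if the SAP text is applied as it stands.

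1. Adverse-event percentages combine monotherapy, combination and comparator subjects.
2. Cohort C subjects take no lenvatinib, yet by default they count in the denominator of the lenvatinib-discontinuation table, which dilutes the rate.
3. A mg/day dose intensity may be summarised across drugs given at very different doses.

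The regional split has a related weakness. The protocol names sorafenib as comparator in a China-only paragraph of 9.4.1, which says: "The subject(s) who receive the comparator in the parent study will be enrolled to Cohort C". A descriptive difference between China and Rest of World may therefore reflect drug mix, and without cohort columns a reader could not check.

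**Working it through.** **Text comparison**

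| Item | Protocol | SAP v2.0 |
|---|---|---|
| Grouping of safety analyses | Treatment group (9.7.1.6) | Region and all subjects (2, 4) |
| Role of Cohorts A/B/C | Treatment assignment (Synopsis) | Enrolment definitions only (4.2) |
| Departure recorded | – | None in section 8; the version history discloses the region split but not the loss of the treatment-group split |

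Protocol 9.7.1 says the SAP will add further detail. A different grouping rule is not further detail.

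**Illustration 1: pooling.** The documents state no cohort sizes and no figure to reproduce, so the mixes below are assumptions over 50 subjects, the number initially expected. The rates are the Grade 3-4 rates from Study E7080-G000-205 (Protocol 7), used only as an example. The protocol gives 41 (79%) for lenvatinib, 36 (71%) for lenvatinib plus everolimus and 25 (50%) for everolimus. The only denominators that reproduce those percentages are 52, 51 and 50, and they sum to the stated 153. The rates are then 41/52 = 78.8%, 36/51 = 70.6% and 25/50 = 50.0%.

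Pooled rate = (nA × 0.788 + nB × 0.706 + nC × 0.500) / 50, using unrounded rates.

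| A/B/C | Pooled | Below lenvatinib alone | Above comparator |
|---|---|---|---|
| 45/0/5 | 76.0% | 2.9 points | 26.0 points |
| 30/10/10 | 71.4% | 7.4 points | 21.4 points |
| 10/10/30 | 59.9% | 19.0 points | 9.9 points |
| 5/5/40 | 54.9% | 23.9 points | 4.9 points |

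**Illustration 2: regional contrast.** Suppose the regimen rates are identical in both regions. A region with a monotherapy/combination/comparator mix of 30/10/60% would show 60.7%, and one with 60/30/10% would show 73.5%. The gap of 12.8 points comes from mix alone.

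**Illustration 3: lenvatinib-discontinuation table.** Protocol 7 reports for the Phase 3 thyroid trial that "lenvatinib was discontinued due to AEs in 14.2% of patients". Taking 14.2% as the rate among subjects on lenvatinib, the default denominator shows 14.2% × (50 − nC)/50:

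- nC = 5: 14.2% × 45/50 = 12.8%
- nC = 10: 14.2% × 40/50 = 11.4%
- nC = 20: 14.2% × 30/50 = 8.5%

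**Illustration 4: dose intensity.** In the hepatocellular trial cited in Protocol 7, lenvatinib was given at 8 or 12 mg/day and sorafenib at 400 mg twice daily, which is 800 mg/day. With 45 subjects at 12 mg/day and 5 at 800 mg/day, a pooled mean would be (45 × 12 + 5 × 800)/50 = 4540/50 = 90.8 mg/day, which describes neither drug.

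**The case against.** The strongest reply is that the SAP does not say its summaries are by region only. It adds detail to the protocol, so silence need not repeal the protocol's rule. SAP 12 puts table content in separate shells, where region could sit above treatment columns. That possibility stands and limits the point to what the SAP text specifies. It does not remove the conflict, because the one grouping the SAP states is not the one the protocol states.

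Other objections, and what remains of them:

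- *The protocol never equates treatment group with Cohorts A/B/C.* True, but these are its only treatment grouping. It is also true that Cohorts B and C may each hold more than one drug, so cohort columns reduce the pooling without always removing it.
- *SAP 6.3 allows a footnoted alternative denominator.* It does. The dilution figures assume that this is not used, and the SAP does not say that it will be.
- *The China-only paragraph does not confine Cohort C to China, and no inferential regional comparison is planned.* Both are correct. The confounding is a possibility, not a demonstrated fact.
- *The illustrative rates come from other populations, and rollover subjects are selected for having tolerated treatment.* This stands. The rates show the mechanism and do not predict results.
- *The version history discloses the regional decision, and Protocol 9.7.5 leaves the description of SAP revisions to the study report.* It discloses the added split, not the loss of the treatment-group split.
- *The study is descriptive, has full listings and expects about 50 subjects initially.* This limits the harm. It does not explain dropping a stated rule without comment.

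**Conclusion.** The concern holds and should be fixed before the tables are produced. On the text, with high confidence, SAP v2.0 specifies a grouping that differs from Protocol 9.7.1.6 and does not record the departure. The specified tables would not show safety by regimen. Overall incidence and the subject listings remain, although the only dosing listing named is for lenvatinib.

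The numerical effect depends on cohort sizes that the documents do not give. It is small when one cohort dominates (2.9 points at 45/0/5) and large when comparator subjects are numerous (23.9 points at 5/5/40). Both figures rest on borrowed rates. If the unseen shells already carry cohort columns, what remains is a correction to the SAP text.

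**What to change.** - In SAP 4 and 6.5, state that exposure and adverse-event summaries are presented by Cohort A, B and C, as the treatment groups of Protocol 9.7.1.6. Use region as a secondary split where numbers allow, and keep the all-subject column as descriptive.
- In SAP 6.5.1, state that mg/day dose intensity is summarised separately by drug.
- In SAP 6.5.2, restrict the denominator of the lenvatinib-discontinuation table to subjects receiving lenvatinib.
- In SAP 8, record the added region split. If cohort columns are left out on purpose, state and justify that departure there.

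The cost is a few lines of text and some extra columns, since every subject is already assigned to a cohort at entry. The drawback is sparse cells. With no events in n subjects, the exact two-sided 95% upper limit is 1 − 0.025^(1/n): 7.1% for n = 50, 30.8% for n = 10 and 52.2% for n = 5. Very small cohort-by-region cells may be better shown as listings.
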